5.6. Treatment Compliance

Patients will be required to return all bottles of olaparib as well as the completed patient diary at the beginning of each cycle for drug accountability. Drug accountability will be performed on day 1 of every 28-day cycle (+/- 7 days) prior to dispensing drug supply for the next cycle. The number of remaining tablets of olaparib will be documented and recorded. Compliance will be assessed by the tablet count and the information should be recorded in the appropriate section of the eCRF.

The patient number should be recorded on the bottle label at time of assignment to a patient. Site personnel must ensure that patients clearly understand the instructions on how and when to take their study treatment. Patients will self-administer study treatment. Patients should be given a sufficient supply to last until their next study visit. Unused drug and/or empty bottles should be returned to the site at the next visit. The remaining tablets will not be returned to the patient, but will be retained by the investigative site, the site must obtain authorization from the Sponsor before destroy it.

Dose adjustments must follow instructions provided in the dose adjustment guidelines section.

6. Efficacy and Safety Evaluations, Sample Collection and Testing (Standard Laboratory Testing) and Appropriateness of Assessments

Study procedures and their timing (including tolerance limits for timing) are summarized in the Study Schedule, Protocol Attachment 1.

6.1. Efficacy Assessments

All assessments to be performed at baseline and during the study are specified in the Study Schedule, Protocol Attachment 1.

According to RECIST v.1.1 in case of patients with a global deterioration of health status requiring discontinuation of treatment without objective evidence of disease progression at that time every effort should be made to document objective progression, even after discontinuation of treatment. The objective response status of such patients should be determined considering RECIST v.1.1 instructions, regarding situations where not all basal lesions can be evaluated. In case any efficacy assessment can be done they will be considered not evaluable for those efficacy endpoints applicable.

6.1.1. Primary Efficacy Assessments

The primary efficacy variable is Objective Response Rate (ORR).

Tumour response will be assessed using RECIST v.1.1. Tumour assessment will be performed at baseline; the same method of measurement used at baseline will be used for further assessments, which will be conducted every 8 weeks (+/- 1 week). Responses should be confirmed according to RECIST v.1.1 after at least 28 days.

The best response across treatment will be recorded. ORR is defined as the percentage of patients with a complete or partial response out of the total of patients in the considered study population (refer to section 8.2.1. Patient Populations).

6.1.2. Secondary Efficacy Assessments

Secondary efficacy assessments are PFS, CBR, RD, and OS:

- ✓ Progression Free Survival (PFS): is defined as the time from study enrolment to the first documented progressive disease, using RECIST version 1.1., or death from any cause, whichever occurs first.
- ✓ Clinical Benefit Rate (CBR): is defined as complete response (CR), partial response (PR), or stable disease (SD) ≥ 24 weeks according to the RECIST version 1.1.
- ✓ Response Duration (RD): is defined as the time from the first documentation of objective tumour response (CR or PR) to the first documented progressive disease using RECIST version 1.1, or to death due to any cause, whichever occurs first.
- ✓ Overall Survival (OS): is defined as the time from the date of study enrolment to the date of death from any cause.

6.2. Safety Assessments

Investigators are responsible for monitoring the safety of patients who have entered this study and for alerting GEICAM of any event that seems unusual.

The Investigator is responsible for appropriate medical care of patients during the study.

The Investigator remains responsible for following, through an appropriate health-care option, adverse events that are serious or that caused the patient to discontinue before completing the study. The patient should be followed until the event is resolved or explained. Frequency of follow-up evaluation is left to the discretion of the Investigator.

During the course of the study, all patients entering the trial must be evaluated according to the schedule outlined in the flow charts and described below. The results of the evaluation will be recorded in the eCRF pages until the patients are not followed anymore.

6.2.1. *Timing of Assessments*

All assessments to be performed at baseline and during the study are specified in the Study Schedule, Protocol Attachment 1.

Physical examination will include vital signs assessments (**blood pressure, pulse and body temperature**) and **performance status** evaluation. Clinical signs and symptoms of disease recurrence should be further investigated as appropriate.

Resting 12-lead ECGs are required within 7 days prior to starting study treatment and when clinically indicated.

Twelve-lead ECGs will be obtained after the patient has been rested in a supine position for at least 5 minutes in each case. The Investigator or designated physician will review the paper copies of each of the timed 12-lead ECGs on each of the study days when they are collected.

ECGs will be recorded at 25 mm/sec. All ECGs should be assessed by the Investigator as to whether they are clinically significantly abnormal / not clinically significantly abnormal. If there is a clinically significant abnormal finding, the Investigator will record it as an AE on the eCRF. The original ECG traces must be stored in the patient medical record as source data.

The following **safety laboratory assessments** will be performed by the local laboratories, at the times specified in the Study Schedule:

- **Haematology:** Full haematology assessments for safety (haemoglobin, red blood cells [RBC], platelets, mean cell volume [MCV], mean cell haemoglobin concentration [MCHC], mean cell haemoglobin [MCH], white blood cells [WBC], absolute differential white cell count [neutrophils, lymphocytes, monocytes, eosinophils and basophils] and absolute neutrophil count or segmented neutrophil count and band forms) should be performed at each visit and when clinically

indicated. If absolute differentials are not available % differentials should be provided. Study visits for safety assessments will be scheduled on baseline visit and day 8 (+/- 3 days) of cycle 1 and in subsequent cycles every 28 days (+/- 7 days). This analysis should be performed also in the 30-day post-discontinuation follow-up evaluation performed 30 days (+/- 7 days) following the discontinuation of study treatment. In case the beginning of this new therapy cannot be delayed as per the investigator's judgment, the safety visit may be performed in advance, but always before starting with the new anticancer therapy.

If treatment is discontinued close to the theoretical date for the next cycle and it is not planned to perform in advance the post-treatment visit due to the initiation of a new anticancer therapy, a new haematology analysis should be performed at the moment of the study treatment discontinuation.

- **Coagulation testing:** Activated partial thromboplastin time (aPTT) and international normalised ratio (INR) will be performed at baseline and if clinically indicated unless the patient is receiving warfarin. Patients taking warfarin may participate in this study; however, it is recommended that prothrombin time (INR and aPTT) be monitored carefully at least once per week for the first month, then monthly if the INR is stable.
- **Blood Chemistry:** sodium, potassium, calcium, magnesium, fasting glucose, creatinine, total bilirubin, gamma glutamyltransferase (GGT), alkaline phosphatase (AP), aspartate transaminase (AST), alanine transaminase (ALT), urea or blood urea nitrogen (BUN), total protein, albumin and lactic dehydrogenase (LDH) should be performed.

In case a subject shows an AST **or** ALT $\geq 3 \times$ ULN **or** total bilirubin $\geq 2 \times$ ULN please refer to Appendix 5 "Actions required in cases of combined increase of Aminotransferase and Total Bilirubin – Hy's Law", for further instructions.

- Similar to haematology test, blood chemistry analysis should be performed on baseline visit, day 8 (+/- 3 days) of cycle 1 and in subsequent cycles every 28 days (+/- 7 days) and if clinically indicated. This analysis should be performed also in the 30-day post-discontinuation follow-up evaluation performed 30 days (+/- 7 days) following the discontinuation of study treatment. In case the beginning of this new therapy cannot be delayed as per the investigator's judgment, the safety visit may be performed in advance, but always before starting with the new anticancer therapy.

If treatment is discontinued close to the theoretical date for the next cycle and it is not planned to perform in advance the post-treatment visit due to the initiation of a new anticancer therapy, a new haematology analysis should be performed at the moment of the study treatment discontinuation.

- **Urinary testing:** Urinalysis by dipstick should be performed at baseline and then only if clinically indicated. Microscopic analysis should be performed by the hospital's local laboratory if required.
- **Serum or urine pregnancy test:** Two pregnancy tests on blood or urine samples must be performed for pre-menopausal women of childbearing potential, one within 28 days prior to the start of study treatment and the other on Day 1 of the study prior to commencing treatment. Tests will be performed by the hospital's local laboratory. If results are positive the patient is ineligible/must be discontinued from the study. In the event of a suspected pregnancy during the study, the test should be repeated.
- **Bone marrow or blood cytogenetic analysis** may be performed according to standard haematological practice for patients with prolonged haematological toxicities as defined in Section 5.4.1.3. Management of Prolonged Haematological Toxicities while on Study Treatment. Bone marrow analysis should include an aspirate for cellular morphology, cytogenetic analysis and flow cytometry, and a core biopsy for bone marrow cellularity. If it is not possible to conduct cytogenetic analysis or flow cytometry on the bone marrow aspirate, then attempts should be made to carry out the tests on a blood sample. If findings are consistent with MDS/AML, study drug should be discontinued and a full description of findings should be submitted with an SAE report by the Investigator to GEICAM for documentation on the Patient Safety database. Presence or absence of blood cytogenetic abnormalities and flow cytometry will be documented on the clinical database.
- Additional analyses may be performed if clinically indicated. All AEs (and their relatedness to the study drugs/medications) occurring during the study will be repeated as clinically indicated and documented in the eCRF. AEs will be graded according to NCI-CTCAE version 4.0.

6.2.2. Definitions

The safety definitions are described in the table 12.

Table 12. Safety definitions

Concept	Definition
Adverse Event (AE)	An adverse event is the development of an undesirable medical condition or the deterioration of a pre-existing medical condition following or during exposure to a pharmaceutical product, whether or not considered causally related to the product. An undesirable medical condition can be symptoms (e.g., nausea, chest pain), signs (e.g., tachycardia, enlarged liver) or the abnormal results of an

	
investigation (e.g., laboratory findings, electrocardiogram). In clinical studies, an AE can include an undesirable medical condition occurring at any time, including run-in or washout periods, even if no study treatment has been administered.
 
The term AE is used to include both serious and non-serious AEs.
 
Laboratory abnormalities should be reported as AE only in case they lead to an action on study treatment or if they are serious.


Adverse Reaction (AR)
	
All untoward and unintended responses to a medicinal product related to any dose administered.
 
All expected ARs are listed in the Investigator's Brochure (IB) in case of not authorized investigational product or Summary of Product Characteristics [SmPC] in case of an authorized investigational product. If the nature or the severity of an adverse reaction is not consistent with the applicable product information, the AR is defined as unexpected. The basis for the decision is the current version of the corresponding reference document that has been submitted and approved by the competent authority and the ethics committees.
 
Accountability criteria
 
The sponsor will classify the adverse event, based in their causation relation with the investigational product, following the Karch and Lasagna algorithm (1977)⁷², as:
 
 • Final: there is reasonable temporal sequence between the drug administration and the existence of the adverse event. This event matches with the adverse reaction described for the investigational product, improves with the omission and reappears after its re-administration and can't be explained by other causes. • Probable: there is reasonable temporal sequence between the investigational product administration and the appearance of the adverse event. This event matches with the adverse reaction described for the drug, improves with the omission and can't be explained by other causes. • Possible: there is reasonable temporal sequence between the investigational product administration and the

	
appearance of the adverse event. This event matches with the adverse reaction described for the drug but can be explained by other causes.
 
 Conditional or improbable: there is reasonable temporal sequence between the investigational product administration and the appearance of the adverse event. This event does not matches with the adverse reaction described for the drug and can be explained by other causes. Not related: there is no reasonable temporal sequence between the investigational product administration and the appearance of the adverse event. This event does not matches with the adverse reaction described for the drug and can be explained by other causes. 
For expedited reporting purposes it is considered as related the categories: final, probable and possible from Karch and Lasagna algorithm (1977) and as not related the category conditional or improbable of that algorithm.
 
The determination of the possible relation with the study treatment is responsibility of the Principal Investigator of the site or the person designated by him.

Serious Adverse Event (SAE) and Serious Adverse Reaction (SAR)	
A serious adverse event is an AE occurring during any study phase (e.g., screening, treatment, wash-out, follow-up), at any dose of the study drugs that fulfils one or more of the following criteria:
 
 Results in death Is immediately life-threatening Requires in-patient hospitalization or prolongation of existing hospitalization Results in persistent or significant disability or incapacity Is a congenital abnormality or birth defect Is an important medical event that may jeopardize the patient or may require medical intervention to prevent one of the outcomes listed above. 
The causality of SAEs (their relationship to all study treatment/procedures) will be assessed by the Investigator(s) and communicated to Pharmacovigilance Department of GEICAM.

	
The following events will be considered as AEs of Special Interest (AESIs) and they have to be documented as a SAE and notified to the Pharmacovigilance Department of GEICAM immediately: Development of MDS/AML, new primary malignancy (other than MDS/AML) and pneumonitis. Overdose and medication errors should be reported as indicated in section 5.4.4. and 11.1.
 
Any temporary increase in the severity of a symptom or previous sickness that happens after the baseline of the study is considered also as an adverse event.

Suspected Unexpected Serious Adverse Reaction (SUSAR)	
Any serious adverse reaction whose nature, intensity or consequences do not correspond with the reference information for the investigational product (example, Investigator Brochure [IB] in case of not authorized investigational product or Summary of Product Characteristics [SmPC] in case of an authorized investigational product).
 
The unexpected nature of an adverse reaction is based in the fact of not being observed previously and not in what could be advanced based on the pharmacological properties of the drug.

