## 9.2.2 Safety Analyses

The toxicity and tolerability of study drugs/medications will be evaluated in the safety population.

Safety analyses will include summaries of the incidence of adverse events (AEs) by maximum NCI-

CTCAE grade (v4.0; NCI 2010) that occur during the study treatment period or within 30 days of the last dose of study treatment, regardless of causality and according to the relationship to study drug/medication as assessed by the Investigator. Additionally, the following safety-related outcomes will be summarized:

- Study treatment discontinuations due to AEs.
- Deaths.
- SAEs and AESIs.
- Hospitalizations and transfusions.
- Use of key concomitant medications or growth factors.

Analyses for data with discrete dates, for example, deaths, transfusions, and concomitant medications, will be done through 30 days after each patient's last dose of study treatment. Adverse events will also be analysed in this timeframe; that is, if an event starts within 30 days of discontinuation from study treatment, but after 30 days after the last dose of study treatment, it will not be included.

Adverse events and SAEs data will be presented in frequency tables by grade. Haematological and clinical biochemistry toxicities will be assessed from laboratory test parameters. The safety analyses will be performed in the safety population.

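### Table 12 of the Protocol counts an event as drug-related only if it matches an already described reaction, so a reaction of a new kind has no route to a related rating

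*Protocol*

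**What the plan says.** Protocol 6.2.2, Table 12 (accountability criteria) gives five categories. All but *not related* presuppose a reasonable time sequence.

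- *Final*: "This event matches with the adverse reaction described for the investigational product, improves with the omission and reappears after its re-administration", with no other cause.
- *Probable*: "This event matches with the adverse reaction described for the drug, improves with the omission and can't be explained by other causes".
- *Possible*: "This event matches with the adverse reaction described for the drug but can be explained by other causes".
- *Conditional or improbable*: "This event does not matches with the adverse reaction described for the drug and can be explained by other causes".
- *Not related*: the same two conditions as *conditional or improbable*, but without plausible timing.

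The table then draws the cut: "For expedited reporting purposes it is considered as related the categories: final, probable and possible". The fourth category counts as not related.

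The SUSAR row of the same table covers serious adverse reactions that in nature, intensity or consequences "do not correspond with the reference information for the investigational product". It rests unexpectedness of nature on the reaction not having been seen before. An adverse reaction is itself defined as a response related to a dose.

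Table 12 first has the sponsor classify with this algorithm, then makes the site's principal investigator or a designee responsible for determining the relationship. Protocol 6.2.3 tells the investigator to use the same algorithm for adverse events, and the eCRF records causality as yes or no. SAP 9.2.2 summarises adverse events "regardless of causality and according to the relationship to study drug/medication as assessed by the Investigator".

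**The concern.** A causality scale and an expectedness test answer different questions: did the drug cause this, and was it already known? Table 12 builds the second question into the first, because being already known is a condition of being rated related. Expedited reporting exists largely for reactions that are both caused by the drug and not yet known, and a literal reading of the scale leaves no room for that combination.

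Adverse events are a secondary endpoint, and the trial gives olaparib to a population selected in a new way. If sites follow the written criteria, the drug-related tables in SAP section 10 (3.1.3, 3.1.5, 3.1.8 and 3.1.10) would contain only reactions of kinds already on record. Serious events of a new kind would also lack the related rating on which SUSAR status depends.

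**Working it through.** No arithmetic is at stake. The check crosses the three criteria that recur in the scale: T, reasonable timing; M, match with a described reaction; O, another cause can explain the event.

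**Non-matching events (M = no)**

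| T | O | Category in Table 12 | Counts as |
|---|---|---|---|
| yes | yes | conditional or improbable | not related |
| yes | no | none fits | unclassified |
| no | yes | not related | not related |
| no | no | none fits | unclassified |

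Result: 0 of 4 related, 2 of 4 not related, 2 of 4 without a category. The second row is the profile most suggestive of a new reaction, and the scale is silent on it.

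**Matching events (M = yes)** reach a related category only when T = yes. With another cause the rating is *possible*. Without one it is *final* or *probable*, both of which also require improvement after stopping. Every related rating therefore needs T = yes and M = yes.

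**Against the SUSAR definition.** A SUSAR is a reaction, so it must be related, and under the scale that requires M = yes. If it is unexpected by nature because it was never observed before, it cannot already be described, so M = no. No event meets both conditions. A described reaction that is unexpected only in intensity or consequences keeps M = yes and can still become a SUSAR.

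**Against the Protocol's other causality tests.**

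- Attachment 4, for serious events in long-term follow-up, asks the investigator whether a causal link to the product or a protocol procedure is reasonably possible. It asks for no match.
- Attachment 5, section 5, assigns a related rating to a Hy's Law case because no alternative explanation exists. Again no match is needed. Under Table 12, the same reasoning applied to any other undescribed event leads to no category.

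**Where the rating has consequences.**

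1. SUSAR notification (Protocol 6.2.5) depends on relatedness.
2. Of the twelve tables numbered 3.1.1 to 3.1.12 in SAP section 10, four are explicitly drug-related: 3.1.3, 3.1.5, 3.1.8 and 3.1.10. They inherit the defect to the extent that the yes/no eCRF item follows the algorithm prescribed in Protocol 6.2.3. Neither document states that mapping.
3. More than 30 days after the last dose, serious events are reportable only if considered related (Protocol 6.2.4; Attachment 4). MDS/AML and new primary malignancy are the exceptions, reportable whatever the causality (Protocol 6.2.3; Attachment 4). A late serious event of another, undescribed kind, rated by Table 12, may not reach the sponsor.

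**The case against.** The strongest reply is that the scale is not the only safeguard, and much of that reply stands. All serious events from first dose to 30 days after the last dose go to the sponsor whatever their rating, and the sponsor may itself suspect a SUSAR (Protocol 6.2.4). AESIs are notified regardless of causality. SAP 9.2.2 also summarises events regardless of causality, and sponsor experts review non-serious events, laboratory, vital-sign and ECG data (SAP 9.2.2.1). A reader might infer that the trial cannot identify new toxicity or that SUSAR detection fails altogether. The documents do not support either inference.

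A reader might also infer that an undescribed event with no other cause would be labelled not related. It would not: both non-matching categories require that another cause can explain the event, so it is left unclassified.

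Pneumonitis and MDS/AML, absent from Protocol Table 5, might seem ready examples of events barred from a related rating. They are weak ones. Protocol 1.6.1 discusses both in olaparib-treated patients, the Investigator's Brochure is not available here, and Table 5 is nowhere named as the standard for what is described. A site could reasonably treat both as described, although Protocol 1.4.5 says the data do not support a causal conclusion.

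A further reply is that described for the drug and listed in the reference document need not mean the same, so an event could be described yet unlisted. That is fair for such events, but it does not help a reaction never seen before.

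Finally, the related/not-related cut is stated for expedited reporting, and the yes/no item leaves room for judgement. But Protocol 6.2.3 ties the investigator's judgement to this algorithm, and Table 12 has the sponsor classify by it too. Sponsor review therefore applies no different written criterion.

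**Conclusion.** The concern holds as a defect of the written rule. A match with a described reaction is necessary for every related category, so a reaction of an undescribed kind can never be rated related: 0 of 4 non-matching profiles. The scale is also incomplete, since 2 of those 4 have no category. It contradicts the SUSAR definition for reactions unexpected by nature, as well as the causality tests in Attachments 4 and 5.

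The reach is limited to three places: the causality step for SUSARs; the four drug-related tables, conditional on the unstated eCRF mapping; and serious events arising more than 30 days after the last dose, other than MDS/AML and new primary malignancy. The primary endpoint, sample size and two-stage decision rule are untouched.

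The conclusion assumes that Table 12 is applied as worded. The source of the cited algorithm was not available, so nothing here rests on its original form. How many events would be misrated cannot be estimated from the documents.

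**What to change.** In Protocol Table 12:

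1. Remove the match with a described reaction as a necessary condition for *final*, *probable* and *possible*.
2. State that an event with reasonable timing and no sufficient other explanation is at least *possible*, whether or not it is described.
3. Redefine *conditional or improbable* as reasonable timing with another cause as the more likely explanation. If it is left unamended, a well-timed, non-matching event with another possible cause could fall into both it and the widened *possible*.
4. Keep expectedness against the Investigator's Brochure or SmPC as a separate, later step.
5. State how the five categories map to the yes/no eCRF item, so that the drug-related tables have a defined source.
6. Settle whether the sponsor, the investigator or both classify. Table 12 opens with the sponsor; its closing statement and section 6.2.3 name the investigator side.
7. Reconcile the tests in Attachments 4 and 5 with the revised scale.

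The cost is a wording change to the Protocol and site instruction. The downside is that some additional events will be rated related and reported.
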